5.1.2 Key informant interviews

Approximately 45 participants will be selected purposively through snowball sampling for the KIIs (PS201). MLW-LSHTM, using their professional networks and PSI country staff, will identify appropriate stakeholders. Interviews will be with written informed consent, will use semi-structured questionnaires and will be audiotaped.

5.1.3 Village selection and community mapping

Primary care clinics and evaluation villagers will be selected in consultation with the program lead for PSI's CBDA programme, and in consultation with the relevant District Health Offices, Primary care clinics and the CBDAs themselves.

Once villages have been selected, preliminary mapping exercises will be initiated including demarcation of the village boundaries and location of dwellings with geographical position system (GPS) and a brief household-level questionnaire (name of household head, demographics of household members).

Sensitisation will include village-level meetings, as well as introduction of the project to village health committees, village governance bodies (e.g., traditional councils), community peer groups, and community-based organisations engaged in HIV and other social services. Membership size and gender and age structure of active community peer-groups (church groups, sports, micro-finance etc) will also be listed during sensitisation.

5.1.4 Pilot study of uptake and accuracy

Two villages not included in the main study will be selected from rural Blantyre or Machinga for pilot studies of accuracy and acceptability. From these villages, 200 to 250 participants in total will be recruited from either randomly selected households (n = 150-200) or community peer groups (n = 48) for the accuracy and acceptability studies.

Peer group members

Two peer groups identified during community mapping exercises will be purposively selected from each of the villages to participate in FGDs (PS301) on HIVST. The groups should broadly represent men, women and youth. Written consent will be required by members in order to participate in the FGDs. Should a peer group refuse, another group will be selected to take its place.

Each FGD will consist of 8 to 12 individuals (n = 48). FGDs will cover barriers and motivators to self-testing and linkage to care as well as group-based dynamics around information sharing and HIVST demonstration. The FGDs will also assess background preferences for service delivery and linkage to care approaches and identify the most salient service attributes that drive decision-making.

Randomly selected households

In addition, 150 to 200 adults will be recruited from a random selection of 60 to 80 households (with an estimated 2-5 adults per household) using randomly selected GPS waypoints. All household members aged 16 years or older will be asked for written consent to answer a brief questionnaire (socio demographics, past HIV testing experience, chronic care including ART) and will be offered HIVST followed immediately by confirmatory HTC (PS303A). Parental consent will be taken for 16 and 17-year-olds and witnessed thumbprint for individuals unable to read or write.

Offer of HIVST and exit interviews

Participants who opt to self-test as well as undergo standard HTC will be given a HIVST kit and a test results forms to record their own reading of the results (PS303B). They will then be provided with a demonstration and instructions before carrying out the self-test

procedure in a private room and completing the test results forms. Participants who themselves recognise that they have made a user error or find that their first result is uninterpretable will be given a second test kit to repeat the procedure if they wish to do so.

Following self-testing, trained HTC counsellors will record their own reading of the test kit before completing the standard HTC process (parallel Unigold and Determine finger prick blood) and entering the results of blood-based testing. All patients testing HIV+ve will be referred to HIV care services.

Specimens will not be stored. However, if discordant test results are obtained, the participant will be asked to consent to providing a dried blood spot sample for subsequent laboratory Enzyme-Linked Immunosorbent Assay (ELISA) and ART drug assay.

Finally, all participants will undergo a brief semi-structured exit interview (PS303C/PS303D) exploring the reasons why a particular HTC option was chosen, asking about their self-testing experience. Feedback will be sought to improve piloted information materials and instructions.

Use of pilot accuracy results

Under the most likely range of scenarios (point estimate of accuracy 95% to 98%), then 200 participants accepting HIVST will be sufficient to exclude (at p = 0.05) an accuracy of below 90%. If the observed accuracy is as high as 98%, then these numbers would be sufficient to exclude an accuracy of below 95% at p = 0.05.

If accuracy is below 90% then the accuracy component of this study will be repeated after IEC supportive materials have been refined.

5.1.5 In-depth interviews

Following the accuracy study, 40 eligible participants will be identified for in-depth interviews (IDIs) according to the categories listed in the purposive sampling framework. An information sheet on the study will be provided to obtain informed, written consent. Researchers will then move on to the next listed household until a sufficient number of participants have been recruited.

		Villa	ge 1	Villa	ge 2	Total
		Previous testing	No previous testing	Previous testing	No previous testing	
	Aged 16 to 39	2	2	2	2	8
HIV	Aged 40+	2	2	2	2	8
negative	Aged 16 to 39	2	2	2	2	8
	Aged 40+	2	2	2	2	8
HIV positive		2	2	2	2	8
Total		10	10	10	10	40

Figure 8. Stratified IDI framework

The IDI (PS302A/302B) will collect data on perceived barriers and motivators to HTC and linkage to care, as well as HTC preferences. The data will be used to analyse readiness and acceptability of self-testing, user preferences for different self-testing options, and factors influencing HIVST uptake and linkage to onward services in different contexts.

Input will also be obtained for two intended study tools: a component of the baseline household questionnaire that will use pictorial representations of salient attributes for different HTC scenarios, and an illustrated self-completed questionnaire that HIVST participants will be asked to complete during the intervention study.

IDI participants will be presented with the proposed images and self-completed questionnaires and asked what they think they represent. If the pictures are not immediately clear, the concepts will be explained and the images shown again at the end of the IDI to

check for recognition. Over the sequence of the IDIs, the tool will be iteratively adapted until it is suitable for inclusion as a Selection of villages

20 primary care facilities offering ART services across the 5 districts will be included in the intervention. Clinic eligibility will be constrained on a specific set of criteria, including:

- CBDA activity in at least one village within its catchment area.
- Location in a district with relatively high HIV prevalence estimates.
- Well-functioning ART services and operations, as assessed by the Department of HIV and AIDS.

5.2 Cluster enumeration

5.2.1 Definition of the study population

20 primary care clinics offering ART services will be included in the intervention. The broader catchment population required for ART uptake evaluation (10 to 20 villages) will be defined in consultation with the clinic staff and PSI CBDA Project Manager. A catchment area that does not cross District boundaries and does not have major alternative ART providers will be selected if possible.

Following this, one or 2 evaluation villages within the ART clinic catchment area will be selected. Eligibility requirement for the evaluation villages include:

- Location within the catchment area of an eligible ART clinic, with the clinic acting as the most dominant source of ARTs for the village.
- Presence of at least one active PSI CBDA.
- Population of 250 to 500 adults.
- Road access for most/all of the year.
- Sufficient distance and separation from administrative boundaries and other intended evaluation villages to minimise 1) 'contamination' between HIVST and control villages, and 2) missed linkage to events from seeking HIV care at a remote clinic not included in the evaluation.
- Villages delineated by natural boundaries (e.g., rivers, roads, forests, etc.) will be preferentially selected.

5.2.2 Baseline household surveys

All households in the evaluation villages will be visited for enumeration and invited to participate in the baseline household survey (PS401A). Village boundaries will be defined by obtained GPS coordinates.

An appointment will be made to visit the head of household or authorised individual to explain the study. All adults and older adolescents will be asked for verbal consent to participate, with verbal consent from guardians required in the case of adolescents.

As part of the baseline household survey, a household-level questionnaire of household size, age and gender composition, and socioeconomic indicators will be administered. Each adult household member will then be asked for verbal consent to participate in a brief individual questionnaire on demographic characteristics and experience with HIV testing and care.

A random selection of participants will then also be asked for written consent to complete an extended individual questionnaire on sexual behaviour, stigma, and health service utilisation, including costs. A discrete choice module will investigate user preferences for HIV delivery and linkage to care.

One in 4 household survey participants will be randomly allocated to a longer questionnaire (PS401B/PS402A), includes an approach to establishing user preferences by asking participants to make a series of trade-off choices (discrete choice experiment: DCE). Written or witnessed informed consent (or assent with guardian consent in the case of adolescents) will be obtained beforehand. Selection will be determined based on a random number generated by the electronic survey device at the time of the household survey (Choko, et al. 2015).

A post-intervention survey will be conducted with the same evaluation villages 12 months after the start of HIVST services. The post-intervention survey will consist of the household and brief individual questionnaires as well as an additional section on self-testing.

5.3 Randomisation and investigator blinding

Following baseline enumeration, ART clinic-evaluation village pairs will be randomly allocated to the intervention or control arm at a public ceremony using constrained randomisation.

Balls or discs numbered 1-N (where N represents the number of possible randomisation combinations) will be selected from an opaque bag by a stakeholder representative. The selected number will correspond to a pre-specified combination of clinics in Arms A and B.

A second opaque bag containing 2 balls – one for HIVST and one for SOC – will then be used to allocate the arm to the selected combination in a second drawing process. It will not be possible to blind participants, community workers, or their supervisors to the cluster intervention allocation, but all specimens and forms and data analysis conducted by laboratory, data, and health facility staff will be managed without reference to the intervention arm.

Outcome data will not be analysed by intervention arm until the final data analysis after completion of the trial, with the exception of data analysis by an independent statistician for presentation to the Data Safety Monitoring Board.

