1.4 Methodology

A population-based CRT with associated mixed methods sub-studies. The intervention will be delivered through CBDAs, trained by PSI to provide HIVST in their rural villages. 20 ART Clinics and their catchment populations will be randomised to either HIVST or standard of care (SOC) arms. The ~200 CBDAs in the HIVST arm will be trained to provide HIVST (OraQuick ADVANCE HIV I/II test kits, packaged for self-use) along with reproductive health products. CBDAs will provide brief pre-test information and a self-referral form with all kits to facilitated linkage into HIV care and prevention services. Posttest advice will be provided for all who confide positive HIVST results.

Outcomes will be captured at 12 months through:

- 1. Household level surveys (~5,000 adults) at baseline and after 12 months of intervention .These will include questions on recent HIV testing through any modality (**Primary Outcome**).
- 2. ART clinic records to investigate whether or not population-level demand for ART has increased (**Secondary Outcome**).

A second stage randomisation of HIVST CBDAs will further explore the role of homebased HIV care assessment for encouraging disclose of positive HIVST results and ART initiation. This is an implementation research study, and no biological specimens will be required for research other than for pilot accuracy evaluation.

The study will be preceded by pilot studies to test the ability to interpret pictorial instructions and accurately use and interpret HIVST kits (packaged with instructions in Chichewa). The trial will be accompanied by economic evaluations. Interviews with key informants will be used to explore the policy and regulatory landscape for HIVST. Tools developed for the main study will be evaluated in other community volunteer cadres, notably voluntary medical male circumcision mobilisers.

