2.3 UNITAID/PSI HIV STAR project

The UNITAID/PSI HIV STAR project will conduct HIVST implementation research to generate the evidence base required for WHO guidelines in Malawi, Zambia and Zimbabwe. The project has a dual focus on marginalised sections of the general population (defined by poor coverage of HTC under current strategies) and key populations (i.e., FSWs, MSM).

Collaborators include WHO, Population Services International (PSI), London School of Hygiene and Tropical Medicine (LSHTM), Liverpool School of Tropical Medicine (LSTM), and University College London (UCL).

PSI is responsible for HIVST implementation, while LSHTM, in conjunction with local partners (the Malawi-Liverpool-Wellcome Trust Clinical Research Programme (MLW) in Malawi) is responsible for implementation research. WHO will lead the development of policy and regulatory guidelines around HIVST.

The funding body for the UNITAID/PSI HIV STAR project is UNITAID, a United Nations organisation housed within WHO that supports the development and optimisation of robust, high-quality and low-cost products specifically intended to meet the diagnostic and pharmaceutical needs of HIV, tuberculosis (TB) and malaria programmes in low-resource countries.

Figure 1. HIV STAR Project Organogram

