4.3 Primary and secondary outcomes

4.3.1 Primary Outcome for main HIVST versus SOC CBDA intervention

The primary outcome is: Comparison between randomisation arms in coverage of recent (within the last 12 months) HIV testing among adult (16 years and above) village residents 12 months after the initiation of the intervention.

A related pre-specified analysis is to compare between randomisation arms the coverage of ever (lifetime) HIV testing among adult (16 years and above) village residents.

These analyses will be based on household surveys carried out in the pre-defined evaluation villages in each randomisation arm.

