Pilot extended baseline questionnaire and revise based on feedback	PI/PM	PSI/MLW																					
Conduct extended baseline questionnaire	PM/PI	PSI/MLW										1											
Conduct quality and accuracy checks on incoming electronic data	PI/DM	MLW																					
Clean quantitative data	DM/PI	MLW										Ì											
Conduct preliminary analysis of quantitative data	PI/LC/MN	MLW/LSHTM										Ì											
Generate preliminary report on baseline findings	PI/LC	MLW																					
Conduct in-depth analysis of quantitative data	PI/LC/MN	MLW/LSHTM																					
Generate in-depth report on baseline findings	PI/LC	MLW																					
Collect and analyse data for interim household survey																							
Pilot extended interim household survey and revise based on feedback	PI/PM	PSI/MLW																					
Conduct interim household survey	PM/PI	PSI/MLW																					
Conduct quality and accuracy checks on incoming electronic data	PI/DM	MLW																					
Clean quantitative data	DM/PI	MLW																					
Conduct preliminary analysis of quantitative data	PI/LC/MN	MLW/LSHTM																					
Generate preliminary report on interim findings	PI/LC	MLW																					

	1	1	1	 	-	1	1	() (1	ſ	 	1			i	1	
Conduct in-depth analysis of quantitative data	PI/LC/MN	MLW/LSHTM		 								 						
Generate in-depth report on interim findings	PI/LC	MLW																
Collect and analyse data from CBDAs and ART clinics																		
Pilot CBDA tools in intervention villages and revise																		
based on feedback	PI/PM	MLW/PSI		 														
Collect SCQs and HIVST registers and kits from CBDAs in intervention villages	PI/PM/CC	MLW/PSI																
Collect harms monitoring records from community	PI/PIVI/CC	IVILVV/P3I										 						
leaders in intervention villages	PI/PM/CC	MLW/PSI																
Collect patient registers and referral forms from ART	, ,																	
clinics	PI/PM/CC	MLW/PSI																
Enter paper-based data into electronic files	DM	MLW																
Conduct quality and accuracy checks on incoming																		
electronic data	PI/DM	MLW		 	_													
Clean quantitative data	DM/PI	MLW																
Conduct preliminary analysis of quantitative data	PI/LC/MN	MLW/LSHTM																
Generate preliminary report on impact evaluation									Ì									
findings	PI/LC	MLW		 														
Conduct in-depth analysis of quantitative data	PI/LC/MN	MLW/LSHTM																

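### The primary outcome is unverified self-report from a survey that the implementing organisation helps to conduct, and section 5.3 leaves the masking of interviewers unclear

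*Protocol*

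**What the plan says.** **Outcome.** Protocol 4.3.1 defines the primary outcome as "coverage of recent (within the last 12 months) HIV testing among adult (16 years and above) village residents 12 months after the initiation of the" (…), so the time point is counted from the start of HIVST delivery. On the source of the data it adds: "These analyses will be based on household surveys carried out in the pre-defined evaluation villages in each randomisation arm". Section 1.4 describes the surveys: "These will include questions on recent HIV testing through any modality". It also says that "no biological specimens will be required for research other than for pilot accuracy evaluation". The sensitivity analysis in 5.8.3 deals with missing answers, not wrong ones.

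**Follow-up interview.** Under 5.2.2 it repeats the household and brief individual questionnaires "as well as an additional section on self-testing".

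**Masking.** Section 5.3 says that participants, community workers and their supervisors cannot be blinded, and then that "all specimens and forms and data analysis conducted by laboratory, data, and health facility staff will be managed without reference to the intervention arm". Interviewers are named in neither group. The staffing table in the addendum lists data collectors under data management.

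**Who does what.** Section 2.3 states that "PSI is responsible for HIVST implementation" and gives implementation research to LSHTM with MLW. In the work plan (section 14), the row "Conduct interim household survey" has PM/PI as lead and PSI/MLW as group. The rows for enumeration and for the extended baseline questionnaire carry the same entries. The rows for checking and cleaning the survey data list MLW without PSI. The PM role also appears in the row for training CBDAs.

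**The concern.** What a respondent tells an interviewer is the primary endpoint. Respondents know whether kits were offered in their village, and an interviewer may know the arm or learn it from the self-testing section. If the people asking are connected with the organisation that supplied the kits, respondents in HIVST villages may report a test out of courtesy, or may be prompted towards one.

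Any such excess in the HIVST arm adds directly to the apparent effect. More clusters or more participants would not remove it. The Protocol describes no link between survey answers and another record that would reveal it.

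**Working it through.** **Inputs.** From section 7.2 and Figure 10: 250 adults per cluster (m), k = 0.25, 80% power, 5% type I error, control coverage 25% to 40%, 10 clusters per arm planned. From 5.8.5: a t test on log cluster risks with 18 degrees of freedom. The misreporting shifts are assumptions, because the Protocol gives none.

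**Step 1: reproduce the plan's figure (30% v 45%).**

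c = 1 + (1.960 + 0.842)² × [p0(1−p0)/m + p1(1−p1)/m + k²(p0² + p1²)] / (p1 − p0)²

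= 1 + 7.849 × (0.00084 + 0.00099 + 0.01828) / 0.0225 = 8.02 clusters per arm, and 2 × 250 × c = 4,007.8 participants. Figure 10 gives 8.02 and 4007.80. The sample size is not in dispute.

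**Step 2: one null trial with a 5-point shift (30% true in both arms, 35% reported under HIVST).**

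Variance of a log cluster risk: v(p) = k² + (1−p)/(mp).

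- v(0.30) = 0.0625 + 0.70/75 = 0.07183
- v(0.35) = 0.0625 + 0.65/87.5 = 0.06993
- SE = √[(0.07183 + 0.06993)/10] = 0.1191
- Non-centrality = ln(0.35/0.30)/0.1191 = 1.295
- Critical t (18 df) = 2.101
- Probability of p < 0.05 = 23%, against a nominal 5%

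**Step 3: across the stated control range.** The threshold is the shift at which ln(p1/p0) = 2.101 × SE. The last column is that shift divided by (1 − p0).

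| Control | +3 points | +5 points | +8 points | Shift at p = 0.05 | RR there | Share of untested adults reporting a test |
|---|---|---|---|---|---|---|
| 25% | 14% | 30% | 59% | 7.2 points | 1.29 | 10% |
| 30% | 12% | 23% | 47% | 8.5 points | 1.28 | 12% |
| 35% | 10% | 19% | 38% | 9.8 points | 1.28 | 15% |
| 40% | 9% | 16% | 32% | 11.1 points | 1.28 | 18% |

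A simulation with 20,000 runs (normal cluster proportions, binomial sampling; 30% control, 5-point shift) gave 21% against 23%, so the formula is slightly high but close.

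**Step 4: where there is a true effect.** With a true 30% v 45%, a 5-point shift moves the risk ratio from 0.45/0.30 = 1.50 to 0.50/0.30 = 1.67. With a modest true effect of 30% v 36%, suppose 5% of the untested 64% misreport. That adds 3.2 points and lifts the chance of significance from 31% to 57%.

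**Step 5: dependence on k.** If k were 0.15 (an assumption, not in the Protocol), the threshold would fall to 4.7-6.8 points, and a 5-point shift would give significance in 32-56% of null trials.

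**The case against.** Several parts of the other side's case stand.

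- **A reader might infer that PSI leads the survey.** The work plan does not show that. It lists PSI and MLW jointly, with the PI as co-lead. PM is not spelled out in the pages available, and the order of names proves nothing. No passage says that CBDAs or their supervisors interview. The row refers to an interim survey; I take it to be the 12-month survey because the CRT part of the work plan lists no other household survey after baseline.
- **A reader might infer that interviewers are outside the masking.** Section 5.3 is ambiguous rather than exclusive, since data staff may include the data collectors in the addendum. Even so, the sentence governs how forms and analysis are handled. It does not say what the person asking the question knows.
- **The bias need not be confined to one arm.** PSI supports CBDAs in both arms (4.1), and every evaluation village must have an active one (5.2.1). Courtesy towards PSI could therefore be partly equal. What differs is kit supply, along with supervisors' home visits to recent self-testers (5.6.3).
- **Question order may already be settled.** The self-testing items are an added section, and the questionnaires sit in appendices not in the available text.
- **Other records exist.** Logbooks and returned kits (5.6.1) could bound plausible self-testing. They are described as process data from HIVST distribution, are not linked to survey answers, and do not cover clinic testing. ART initiation comes from clinic registers but is the secondary outcome.
- **Masking has limits.** Allocation is drawn at a public ceremony and kits are offered openly.

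**Conclusion.** The concern holds as a weakness in how the primary outcome is collected. The outcome is self-report with no stated verification, the implementer jointly conducts the survey despite the division of roles in section 2.3, and 5.3 does not settle what interviewers may know.

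The tempting stronger conclusion, that a small reporting shift would create a positive trial, is not supported. At the plan's k of 0.25, a 3-point shift leaves 86-91% of null trials non-significant and a 5-point shift leaves 70-84%. A false positive becomes more likely than not only at about 7 to 11 points, when 10-18% of untested adults report a test they did not have. What smaller shifts do is raise the error rate (to 9-14% at 3 points and 16-30% at 5 points), inflate the risk ratio, and help a modest true effect over the line.

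These figures assume that over-reporting occurs in the HIVST arm only. Any equal over-reporting in the SOC arm would reduce them, and a k below 0.25 would increase them. How much misreporting to expect cannot be determined from the Protocol.

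**What to change.** State the following in 5.2.2 and 5.3, and correct the work plan to match:

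1. The 12-month survey is run under MLW.
2. No one with a role in kit distribution, CBDA training or CBDA supervision conducts or attends an interview.
3. Each interviewer works in villages of both arms and is not told allocation. Section 5.3 names interviewers explicitly.
4. The 12-month testing question keeps its baseline wording and comes before the self-testing section.

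The outcome, the sample size and the number of interviews do not change. The cost is some extra travel and scheduling within the planned survey team. The Protocol gives no interviewer numbers, so whether MLW's own staff could take every interview is unknown, and the change does not require that. Masking will remain imperfect, but who interviews, how interviewers are spread over the arms, and the order of questions can all be fixed before fieldwork.
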